			To include the multicomponent endpoint in the hierarchy to address the health authority's feedback requesting assessment of this endpoint as another measure of treatment success.
			To explore the robustness of the estimate, and the inference thereof, with a different strategy for handling intercurrent events and missing data

SAP Version	Approval Date	Changes	Rationale
		Remove "selected" in the text including "selected prohibited and/or rescue medication"	Since a participant who takes any protocol specified prohibited medications/procedures and/or rescue medications is considered as a non-responder after medical adjudication/confirmation conducted in a blinded fashion, use of the word "selected" may be confusing.
		Add Appendix 7 back in Section 5.7	Add this medication/procedure adjudication algorithm back as it was inadvertently removed in SAP Version 2.
4.0	11-Nov-2021	
To promote the "proportion of participants with improvement (reduction) in worst-itch numeric rating scale (WI-NRS) by ≥ 4 from baseline to Week 24 as primary endpoint and to move the "proportion of participants with improvement (reduction) in WI-NRS by ≥ 4 from baseline to Week 12" to a secondary endpoint
 
To update hierarchical order in Section 4.6 by removing "Proportion of participants with improvement (reduction) in WI-NRS by ≥ 4 from baseline to Week 12", "Proportion of participants with IGA PN-S 0 or 1 score at Week 12" and "Change from baseline in Sleep-NRS to Week 24"
	
Based on the data from EFC16460, the treatment effect of dupilumab continued to improve over time through Week 24. Therefore, the Sponsor proposes to assess the proportion of participants with improvement (reduction) in WI-NRS by ≥ 4 at Week 24, which represents the effect more accurately and synchronizes the primary itch assessment with the primary lesion assessment. This is consistent with primary endpoint change in Protocol Amendment 3.
 
Updated power calculations performed using data from study EFC16460 showed low power for demonstrating statistical significance for each of these three endpoints. Accordingly, the hierarchical order was revised to remove these endpoints.

The first participant was randomized on 2020-01-02.

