
 To demonstrate efficacy of dupilumab on skin lesions of PN. 	
 Proportion of participants with Investigator's Global Assessment 0 or 1 score for PN-Stage (IGA PN-S) at Week 24 [Key secondary endpoint]. Proportion of participants with IGA PN-S 0 or 1 score at Week 12. Proportion of participants with IGA PN-S 0 or 1 score at Week 8^c. Proportion of participants with IGA PN-S 0 or 1 score at Week 4^c. Change from baseline in IGA PN-S score at Week 24. Change from baseline in IGA PN-S score at Week 12. Change from baseline in IGA PN-S score at Week 8. Change from baseline in IGA PN-S score at Week 4. Proportion of participants with Investigator's Global Assessment 0 or 1 score for PN-Activity (IGA PN-A) at Week 24. Proportion of participants with IGA PN-A 0 or 1 score at Week 12. Proportion of participants with IGA PN-A 0 or 1 score at Week 8. Proportion of participants with IGA PN-A 0 or 1 score at Week 4.

 To demonstrate efficacy of dupilumab on both itch as well as skin lesions within the same participant 	
 Proportion of participants with both an improvement (reduction) in WI-NRS by ≥ 4 from baseline to Week 24 and an IGA PN-S 0 or 1 score at Week 24 (key secondary endpoint for US and US reference countries only).

 To demonstrate the improvement in health-related quality of life (HRQoL). 	
 Change from baseline in HRQoL, as measured by Dermatology Life Quality Index (DLQI) to Week 24. Change from baseline in HRQoL, as measured by DLQI to Week 12.

 To evaluate safety outcome measures. 	
 Percentage of participants experiencing treatment-emergent adverse events (TEAEs) or serious adverse events (SAEs) from baseline through Week 24.

Objectives	Endpoints

 To evaluate immunogenicity of dupilumab. 	
 Incidence of treatment-emergent antidrug antibodies (ADA) against dupilumab over time.
Tertiary/exploratory	

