
 To demonstrate a reduction in the use of rescue medication and systemic immunosuppressant To evaluate exploratory outcome measures 	
 Use of high potency or superpotent TCS rescue medication through Week 24 Use of systemic immunosuppressants through Week 24, constituting treatment failure Change from baseline in Hospital Anxiety and Depression Scale (HADS) total score to Week 24. Change from baseline in EQ5D-5L to Week 24. Change from baseline in skin Pain numeric rating scale (NRS) to Week 4, Week 8, Week 12, and Week 24, respectively. Change from baseline in Sleep NRS to Week 4, Week 8, Week 12, and Week 24, respectively. Missed school/work days through Week 24. Incidence of skin-infection TEAEs (excluding herpetic infections) through Week 24.

 To evaluate the efficacy of dupilumab on skin lesions using a modified PAS 5-item questionnaire To evaluate the efficacy of dupilumab on other PN endpoints 	
 Proportion of participants who achieve $\geq 75\%$ healed lesions from Prurigo Activity Score (PAS) at Week 4, Week 8, Week 12, and Week 24, respectively. Change from baseline in exact number of lesions in representative area (as determined from PAS) at Week 4, Week 8, Week 12, and Week 24, respectively. Change from baseline in Participant Global Impression of Severity (PGIS) of PN to Week 4, Week 8, Week 12, and Week 24, respectively. Participant Global Impression of Change (PGIC) of PN at Week 4, Week 8, Week 12, and Week 24, respectively.
PK	

 To evaluate pharmacokinetic (PK) and pharmacodynamic (PD) outcome measures 	
 Serum functional dupilumab concentrations and PK profile. Pharmacodynamic response for selected biomarkers (total IgE).

- a The early onset for significant change in the proportion of responders with WI-NRS reduction ≥ 4 between dupilumab and placebo will be claimed at Week xx if the p-value for Week xx is <0.05 and the remaining timepoints also have nominal p-value ≤ 0.05 until Week 12.
- b The early onset for significant change in WI-NRS from baseline between dupilumab and placebo will be claimed at Week xx if the p-value for Week xx is <0.05 and the remaining timepoints also have nominal p-value ≤ 0.05 until Week 12.

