- c The early onset for reaching IGA PN-S (0,1) between dupilumab and placebo will be claimed at Week xx if the p-value for Week xx is ≤ 0.05 and the remaining timepoints also have nominal p-value ≤ 0.05 until Week 12.

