4.6 MULTIPLICITY ISSUES

The multiplicity procedure is proposed to control the overall type-I error rate for testing the primary and selected secondary endpoints. The overall alpha is 0.05. The comparisons with placebo will be tested based on the hierarchical order below at 2-sided $\alpha = 0.05$:

In US and US reference countries:

- Proportion of participants with improvement (reduction) in WI-NRS by ≥ 4 from baseline to Week 24
- Proportion of participants with IGA PN-S 0 or 1 score at Week 24
- Proportion of participants with both an improvement (reduction) in WI-NRS by ≥ 4 from baseline to Week 24 and an IGA PN-S 0 or 1 score at Week 24
- Percent change from baseline in WI-NRS at Week 24
- Change from baseline in HRQoL, as measured by Dermatology Life Quality Index (DLQI) to Week 24
- Change from baseline in skin Pain-NRS to Week 24
- Change from baseline in Hospital Anxiety and Depression Scale (HADS) total score to Week 24

In all other countries (including EU and EU reference countries, as well as Japan):

- Proportion of participants with improvement (reduction) in WI-NRS by ≥ 4 from baseline to Week 24
- Proportion of participants with IGA PN-S 0 or 1 score at Week 24
- Percent change from baseline in WI-NRS at Week 24
- Change from baseline in HRQoL, as measured by Dermatology Life Quality Index (DLQI) to Week 24
- Change from baseline in skin Pain-NRS to Week 24
- Change from baseline in Hospital Anxiety and Depression Scale (HADS) total score to Week 24.

The study is considered positive when the primary endpoint achieves statistical significance.

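### SAP Table 2 footnotes a–c provide for three early-onset claims at unadjusted 0.05, outside both SAP 4.6 hierarchies and not conditional on the Week 24 primary

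*SAP*

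**What the plan says.** SAP 1.2, Table 2, attaches three footnotes to secondary endpoints.

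- **Footnote a** is on the proportion with WI-NRS reduction of at least 4 over time to Week 24. **Footnote b** is on onset of action in WI-NRS change to Week 12. Under both, early onset "will be claimed at Week xx if the p-value for Week xx is <0.05 and the remaining timepoints also have nominal p-value" no greater than 0.05 until Week 12.
- **Footnote c** says "The early onset for reaching IGA PN-S (0,1) between dupilumab and placebo will be claimed at Week xx" on a parallel condition at 0.05. It is attached to "Proportion of participants with IGA PN-S 0 or 1 score at Week 8" and to the matching Week 4 line. The Week 12 line carries no footnote.

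SAP 4.6 sets the scope of error control: "The multiplicity procedure is proposed to control the overall type-I error rate for testing the primary and selected secondary endpoints". It continues: "The overall alpha is 0.05", and "The comparisons with placebo will be tested based on the hierarchical order below at 2-sided" 0.05. Two regional lists follow. Every entry is a Week 24 endpoint and none is an onset endpoint. The study counts as positive on the primary alone.

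The SAP version history (Table 1, version 4.0) records the change "To update hierarchical order in Section 4.6 by removing" three endpoints: WI-NRS response at Week 12, IGA PN-S 0/1 at Week 12, and Sleep-NRS change at Week 24. The reason given is that updated calculations "showed low power for demonstrating statistical significance for each of these three endpoints". The same version moved the primary itch endpoint from Week 12 to Week 24.

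**The concern.** The footnotes do more than define a descriptive summary: they say when a claim will be made. The deciding test is at an unadjusted 0.05, there are three such rules, and no text requires the primary or any hierarchical test to succeed first. Followed as written, the trial could miss its Week 24 primary and still claim early onset of itch or lesion benefit.

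The history explains the gap. While WI-NRS response at Week 12 was the primary and IGA PN-S 0/1 at Week 12 was in the hierarchy, rules a and c ended on tests that had a place in the error-control scheme. Version 4.0 removed that anchor and left the claim wording as it was. Rule b ends on WI-NRS change at Week 12, which was not among the three endpoints removed.

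At stake is whether an onset statement in a report or label discussion carries the error control that readers associate with the word claim.

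**Working it through.** **Inputs from the SAP.** Overall alpha 0.05, two-sided, fixed sequence (4.6). Onset rules and footnote placement (Table 2). About 150 participants, 75 per arm (section 2). **Assumed, because the documents give none:** correlations between the test statistics.

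**1. The stated alpha.** In a fixed sequence with every step at 0.05, the error rate under no effect is that of the first test: 0.05. The SAP's figure is reproduced.

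**2. One footnote alone.** Onset at any week requires every later test up to Week 12 to be significant, so any claim implies p ≤ 0.05 at Week 12. This is a backward fixed sequence. Each footnote's own error is at most 0.05, however many weeks are tested.

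**3. Three footnotes, three readings (no effect, two-sided).**

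- *A: Week 12 can be the onset week for all three.* Each claim has error 0.05. If independent, P(any) = 1 − 0.95³ = 0.143.
- *B: footnote c applies only at Weeks 4 and 8, where it is attached; a and b may start at Week 12.* The IGA claim needs Week 8 and Week 12 both significant. Its error is about 0.009–0.030 for a Week 8–12 correlation of 0.5–0.9.
- *C: onset must precede Week 12 for all three.* Each claim needs two significant tests.

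Simulated P(any), with correlation 0.7 between the two itch statistics and 0.4 between itch and IGA:

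| Correlation between successive tests | A | B | C |
|---|---|---|---|
| 0.5 | 0.123 | 0.091 | 0.025 |
| 0.7 | 0.123 | 0.096 | 0.044 |
| 0.9 | 0.123 | 0.107 | 0.076 |

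With the itch–itch correlation varied from 0.5 to 0.9 and itch–IGA from 0 to 0.6, the ranges are about 0.10–0.14 (A, including independence), 0.08–0.12 (B) and 0.02–0.09 (C). Divided by 0.05, these are about 2.0–2.8, 1.6–2.4 and 0.4–1.8.

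**4. Favourable direction only.** Under A, a false claim in favour of dupilumab has probability about 0.052–0.069 over that grid, against 0.025 for one two-sided test.

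**5. Onset claimed while the primary fails (reading A).** P(primary or any onset claim) minus P(primary), in three individual-level null simulations with 75 per arm:

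- 0.1577 − 0.0488 = 0.1089
- 0.1674 − 0.0514 = 0.1160
- 0.1705 − 0.0500 = 0.1205

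**6. The low figures under C are not a bound.** If there is a true effect at Week 12 that is nearly certain to be detected, and none just before, the Week 12 test no longer protects. Each claim of earlier onset then has error near 0.05, and P(any) moves back towards the figures under A.

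**7. Check of the remedy.** At 0.05/3 = 0.0167 per claim, P(any) cannot exceed 3 × 0.0167 = 0.05. Simulation at correlations 0.7 and 0.3 gives about 0.045. Conditioning on the primary alone lowers the no-effect rate to about 0.014–0.024. It does not control error among the three claims once the primary effect is real.

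**The case against.** The best defence is that the SAP already separates these endpoints. Section 4.4.1 is headed as key or confirmatory, and every endpoint carrying a footnote is listed in 4.4.2 as supportive. Section 4.6 lists what is controlled, and the footnotes call the later p-values nominal. That much stands: a careful reader can tell the controlled tests from the others. It does not settle the point, because the footnotes still prescribe a claim and no sentence says that p-values outside the hierarchy are nominal.

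A reader might infer several stronger things that the documents do not support.

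- *The overall 0.05 is breached.* It is not. Section 4.6 confines it to the primary and the listed secondary endpoints.
- *False onset claims run at a fixed multiple such as 2.5 times alpha.* That figure needs Week 12 to count as an onset week for all three, against the placement of footnote c, together with particular assumed correlations. Under reading C there may be no excess at all when there is no effect.
- *Removing the Week 12 tests raised the error of the onset rules.* It did not. It left rules a and c without a controlled end point.
- *Ending the rule at Week 12 is itself a mistake.* For early onset it is a reasonable horizon. The difficulty is the missing link to Week 24 success.

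**Conclusion.** The point holds as a wording and scope problem with a real consequence: three onset claims at unadjusted 0.05, in neither hierarchy and with no stated condition on the primary. The reading that best fits the footnote placement (B) gives about 0.08–0.12 for at least one false claim. Reading A gives 0.10–0.14 and reading C about 0.02–0.09. All three ranges assume no effect, count both directions and rest on correlations the documents do not supply. The error rate within each footnote is sound, and so is the hierarchy's 0.05. The excess comes only from making three unadjusted claims alongside the hierarchy.

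**What to change.** In SAP Table 2 footnotes a–c, replace the statement that onset will be claimed with: *will be described using nominal p-values; no confirmatory onset claim will be made*. In SAP 4.6, add that p-values for endpoints outside the applicable hierarchy are nominal. These two edits resolve the point under all three readings.

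If the sponsor wants a controlled onset claim, make it conditional on success of the full applicable 4.6 hierarchy. Share alpha among the three claims, for example 0.05/3 each, and test each one backward from Week 12 within its own footnote. A single chain running through every week of one footnote before the next is opened would leave the later claims practically untestable.

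The cost is SAP text before the primary database lock; the descriptive option needs no new data or analyses. The downside is that onset results become descriptive, or claimable only after the whole hierarchy succeeds. The loss for a and c is likely modest, since the sponsor reports low power for the Week 12 tests on which they end.

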1.2.1 Estimands

The primary estimands defined for main endpoints are summarized in below [Table 3](#). More details are provided in [Section 4](#).

Table 3 - Summary of primary estimand for main endpoints

Endpoint Category	Estimands			
	Endpoint(s) ^a	Population	Intercurrent event(s) strategy and missing data handling	Population-level summary
Primary objective: To demonstrate the efficacy of dupilumab on itch response in participants with PN, inadequately controlled on topical prescription therapies or when those therapies are not advisable.				
Primary endpoint	Proportion of participants with improvement (reduction) in worst-itch numeric rating scale (WI NRS) by ≥ 4 from baseline to Week 24	ITT	
The intercurrent events will be handled as follows:
 
 Discontinuation of study treatment before Week 24: Off-study treatment data up to Week 24 will be included in the analysis (treatment policy strategy). Taking the prohibited medications/procedures and/or rescue medications^b prior to Week 24: Participants will be considered as non-responders (composite strategy). 
In addition, the missing data imputation rules are as follows:
 
 Having missing data at Week 24: Participants will be considered as non-responders 	CMH test adjusted by documented history of atopy (atopic or non-atopic), stable use of TCS/TCI (yes or no), region (countries combined), and baseline antidepressant use (yes or no).
Secondary objective: To demonstrate the efficacy of dupilumab on additional itch endpoints in participants with PN, inadequately controlled on topical prescription therapies or when those therapies are not advisable.				
Secondary endpoint	Time to onset of effect on pruritus as measured by proportion of participants with an improvement (reduction) in WI-NRS by ≥ 4 from baseline during the 24-week treatment period	ITT	
The intercurrent events will be handled as follows:
 
 Discontinuation of study treatment before Week 24: Off-study treatment data up to Week 24 will be included in the analysis (treatment policy strategy). Taking the prohibited medications/procedures and/or rescue medications^b prior to Week 24: Analyses will be censored at Week 24 (composite strategy). 
In addition, the missing data imputation rules are as follows:
 
 Discontinuing the study follow-up before Week 24: Analyses will be censored at the time of last WI-NRS assessment. 	
This time-to-event endpoint will be analyzed using the Cox proportional hazards model, including intervention group, documented history of atopy (atopic or non-atopic), stable use of TCS/TCI (yes or no), region (countries combined), and baseline antidepressant use (yes or no). The hazards ratio, its 95% confidence interval and p-value will be reported. Kaplan-Meier curves will be also provided^b

Endpoint Category	Estimands			
	Endpoint(s) ^a	Population	Intercurrent event(s) strategy and missing data handling	Population-level summary
Secondary endpoint	Change from baseline in WI-NRS at Week 24	• ITT	
The intercurrent events will be handled as follows:
 
 Discontinuing the study treatment: all data collected following schedule after treatment discontinuation will be used in the analysis (treatment policy strategy). Taking the prohibited medications/procedures and/or rescue medications^b prior to Week 24: data will be set to missing values after the medication usage, and the participant's worst postbaseline value on or before the time of the medication usage will be used to impute missing endpoint value (for participants whose postbaseline values are all missing, the participant's baseline will be used to impute the missing endpoint value) (hypothetical strategy) 
In addition, the missing data imputation rules are as follows:
 
 After discontinuation of the study treatment due to lack of efficacy prior to Week 24: WOCF approach will be used to impute missing data if needed². After discontinuation of the study treatment due to reasons other than lack of efficacy prior to Week 24: multiple imputation (MI) approach will be used to impute missing endpoint value, and this multiple imputation will use all participants excluding participants who have taken the prohibited medications and/or rescue medications prior to Week 24 and excluding participants who discontinue due to lack of efficacy prior to Week 24. 	ANCOVA model with intervention group, documented history of atopy (atopic or non-atopic), stable use of TCS/TCI (yes or no), region (countries combined), baseline antidepressant use (yes or no), and relevant baseline measurement as covariates is used. Statistical inference obtained from all imputed data by ANCOVA model will be combined using Rubin's rule.

a Additional secondary objectives/endpoints are not included in this table but would be handled with a similar strategy as the endpoint type (ie continuous, proportion, time-to-event) at other weeks

b Prohibited medications and/or rescue medications are listed in [Table 5](#).

2 SAMPLE SIZE DETERMINATION

The primary endpoint is the proportion of participants with WI-NRS reduction of ≥ 4 from baseline to Week 24. By assuming the response rate is [REDACTED] in the placebo and dupilumab arms, respectively, 56 participants/arm will provide 90% power to detect the difference of [REDACTED] between dupilumab and placebo with Fisher exact test at 2-sided level of 0.05. Assuming 15% drop out during treatment, the target is to randomize 75 participants/arm with a cap of up to 10% of participants in the atopic population having active mild AD.

The assumptions were based on the effect of dupilumab versus placebo in WI-NRS reduction ≥ 4 at Week 16 observed in participants with moderate to severe AD as seen in studies of AD-1334 (Solo1) and AD 1416 (Solo2).

Approximately 150 participants will be randomized to dupilumab or placebo in a 1:1 ratio with stratification factors of documented history of atopy (atopic or non-atopic), stable use of TCS/TCI (yes or no), and country/territory code. Both the atopic and the non-atopic PN population will be capped at 60% of the total enrolled population.

The sample size calculation was performed using SAS 9.4 power procedure.

3 ANALYSIS POPULATIONS

The following populations for analyses are defined:

Table 4 - Populations for analyses

Population	Description
Screened	All participants who sign the ICF.
Randomized	The randomized population includes all participants with a treatment kit number allocated and recorded in the interactive response technology (IRT) database, and regardless of whether the treatment kit was used or not. Participants treated without being randomized will not be considered randomized and will not be included in any efficacy population.
Intent-to-treat (ITT)	All randomized participants analyzed according to the intervention group allocated by randomization regardless if treatment kit is used or not
Efficacy	The ITT population
Safety	All participants randomly assigned to study intervention and who take at least 1 dose of study intervention. Participants will be analyzed according to the intervention they actually received. Randomized participants for whom it is unclear whether they took the study medication will be included in the safety population as randomized. For participants who accidentally receive different treatment from the planned, the actual intervention allocation for as-treated analysis will be the dupilumab group. The PD analyses will be performed on the safety population.
Pharmacokinetic (PK)	The PK population includes all participants in the safety population with at least one non-missing result for functional dupilumab concentration in serum after first dose of the study treatment. Participants will be analyzed according to the intervention actually received.
Antidrug antibody (ADA)	ADA population includes all participants in the safety population who have at least one non-missing ADA result after first dose of the study treatment. Participants will be analyzed according to the intervention actually received.

ADA: antidrug antibody; ICF: informed consent form; ITT: intent to treat; PD: pharmacodynamics; PK: pharmacokinetic.

Participants exposed to study intervention before or without being randomized will not be considered randomized and will not be included in any analysis population. The safety experience of these participants will be reported separately.

Randomized participants for whom it is unclear whether they took the study intervention will be considered as exposed and will be included in the safety population as randomized.

For any participant randomized more than once, only the data associated with the first randomization will be used in any analysis population. The safety experience associated with any later randomization will be reported separately.

For participants receiving more than one study intervention (placebo and dupilumab) during the study, the intervention group for as-treated analysis will be the dupilumab group.

Regarding the COVID-19 pandemic, additional summaries by COVID-19 subgroups (ie, impacted by the COVID-19 pandemic and NOT impacted by the COVID-19 pandemic) will be provided to assess the impact of COVID-19 on treatment effect. Participants impacted by the COVID-19 pandemic are defined as randomized participants with any critical or major deviation related to COVID-19 or who permanently discontinued study intervention or study due to COVID-19.

